2 LIST OF ABBREVIATIONS AND DEFINITIONS OF TERMS

ACM	all-cause mortality
AE	adverse event
BMI	body mass index
CABP	community-acquired bacterial pneumonia
CI	confidence interval
CE	clinically evaluable
CN	clinically notable
CT	computed tomography
CXR	chest X-ray
eCRF	electronic case report form
ECR	Early Clinical Response
EMA	European Medicines Agency
EOT	End of Treatment
FDA	Food and Drug Administration
IND	Investigational New Drug
IRB	Institutional Review Board
IV	intravenous
IxRS	Interactive Response System
lpf	Low Power Field
ME	microbiologically evaluable
MedDRA	Medical Dictionary for Regulatory Activities
MDRSP	multi-drug resistant Streptococcus pneumoniae
mg	milligram
MIC	minimum inhibitory concentration
MRSA	Methicillin-Resistant Staphylococcus aureus
MSSA	Methicillin-Susceptible Staphylococcus aureus
NDA	New Drug Application
NI	non-inferior

PNSSP	Penicillin-nonsusceptible Streptococcus pneumoniae
PORT	Pneumonia Outcomes Research Team
PSSP	Penicillin-susceptible Streptococcus pneumoniae
PD	Pharmacodynamic
PK	Pharmacokinetic
PO	orally
PR	Interval from the P wave (atrial contraction or depolarization) to the onset of the Q wave in the measurement of electrical activity of the myocardium
PTE	post therapy evaluation
QTc	QT, corrected
SAE	serious adverse event
SAP	Statistical Analysis Plan
SAS	Statistical Analysis Software
SD	standard deviation
SI	International System
spp	species (plural)
SIRS	Systemic Inflammatory Response Syndrome
TEAE	treatment emergent adverse event
UAT	urinary antigen test
ULN	upper limit of normal
US	United States

3 INTRODUCTION

This document presents the Statistical Analysis Plan (SAP) for the protocol PTK0796-CABP-1200, “A Phase 3 Randomized, Double-Blind, Multi-Center Study to Compare the Safety and Efficacy of Omadacycline IV/PO to Moxifloxacin IV/PO for Treating Community-Acquired Bacterial Pneumonia (CABP).” The statistical plan described is an *a priori* plan and no analysis prior to the preparation of this plan has been conducted. This SAP summarizes the study design and objectives, and provides details of the outcome definitions and statistical methods that will be used to analyze the data from protocol PTK0796-CABP-1200.

The study has been designed to address both the Food and Drug Administration (FDA) and European Medicines Agency (EMA) regulatory requirements; however, a separate SAP will be developed to address the different primary efficacy outcome and analyses for the EMA. While the EMA supports the assessment of clinical response by the Investigator at a Post Therapy Evaluation (PTE) visit (which is scheduled to occur 5 to 10 days after the last dose of test article) as the primary endpoint, the FDA guidelines require using an earlier primary endpoint (Day 3 to Day 5 after the first dose of test article) based on improvement in pneumonia symptoms.

4 TRIAL OBJECTIVES

4.1 Primary Objectives

The primary objective of this study is to demonstrate that omadacycline 100 mg iv once every 12 hours (q12h) for 2 doses, followed by 100 mg iv/300 mg po once every 24 hours (q24h) is non-inferior to moxifloxacin 400 mg iv/po q24h in the treatment of adults with CABP.

4.2 Secondary Objectives

The secondary objectives are as follows:

- To evaluate the safety of omadacycline in the treatment of adult subjects with CABP in the Safety population
- To evaluate the Clinical Response (Early Clinical Response and investigator assessment of response) according to the identified causative pathogen
- To evaluate the pharmacokinetics (PK) of omadacycline in adult subjects with CABP

5 STUDY DESIGN CONSIDERATIONS

5.1 Study Design

This is a randomized (1:1), double-blind, active comparator-controlled, Phase 3 study comparing 7 to 14 days of treatment with either omadacycline or moxifloxacin for the treatment of adults with CABP. The number of subjects in Pneumonia Outcomes Research Team (PORT) Risk Class II will be limited to no more than 15% of randomized subjects. Subject randomization will be stratified across treatment groups by PORT Risk Class (II and III/IV), receipt of an allowed antibacterial therapy in the 72 hours prior to study treatment (yes and no) and geographic region (Western Europe/North America, Eastern Europe, and Rest of World). All subjects are expected to present with CABP severe enough to require a minimum of at least 3 days of intravenous (iv) treatment. After a minimum of 3 days of iv treatment, the investigator can switch the subject to oral (po) treatment if the subject is considered clinically stable and meets the criteria for transition to a po regimen.

Screening assessments will be performed within 24 hours before the first infusion of test article. The day of the first infusion of test article is defined as Day 1 and the day prior is Day-1; there is no Day 0. The study will have the following protocol-defined evaluations:

- Visits will be conducted daily on Days 1 through 7. The Day 6 visit is optional for subjects that have been switched to po test article and have been discharged from a hospital setting. A Day 10 visit should be conducted for subjects with treatment extending beyond 9 days, unless this visit coincides with the End of Treatment (EOT) Visit.
- EOT Visit: to be performed on the calendar day of, or within 2 days following the last dose of any test article. If a subject withdraws prematurely or terminates participation in the study before completion, the EOT Visit should be conducted.
- PTE Visit: to be performed 5 to 10 days after the subject's last day of study therapy
- Final Follow-up assessment: Study Day 30-37 (after start of first infusion of test article)

A detailed Schedule of Study Procedures is provided in [Appendix 1](#).

5.1.1 Sample Size

The study is designed to show NI in the primary efficacy outcome for the FDA of Early Clinical Response (ECR) at 72 to 120 hours following the first dose of test article in the intent to treat (ITT) population. An NI margin of 10% will be used for the analysis in the ITT population. The NI margin was based on an analysis of the historical data regarding the treatment effect of antibiotics in pneumonia.

The study has also been designed to show NI in the co-primary efficacy outcomes for the EMA of Investigator assessment of clinical response at the PTE visit in the ITT and CE-PTE

populations. A separate SAP will be developed to address the different primary efficacy outcome and analyses for the EMA.

In the ceftaroline clinical studies which enrolled only subjects of PORT Risk Class III and IV, the rates for clinical success based on Investigator's Assessment of Clinical Response at the PTE visit ranged from 77%-87% in the modified ITT and clinically evaluable (CE) populations, with the rates in the modified ITT population lower than those in the CE population ([Teflaro, 2013](#)). Thus, it is reasonable to assume clinical success rates of 79% in the ITT and 85% in the CE populations.

For the Investigator's Assessment of Clinical Response at PTE endpoint in the ITT population (PORT Risk Class III and IV) assuming an outcome rate of 79% in both treatment groups, NI margin of 10%, 80% power and a 1-sided alpha level of 0.0125 (since 1 CABP study is being conducted), using the sample size determination method of Farrington and Manning ([1990](#)), a total of 638 subjects (PORT Risk Class III and IV) are required. Assuming an 80% evaluability rate, 510 subjects will be available in the CE population. Assuming an 85% response rate in both treatment groups, a 10% NI margin, 1-sided alpha level of 0.0125, there is 81% power to show NI for Investigator's Assessment of Clinical Response at PTE in the CE population. If 15% of subjects are in PORT Risk Class II, a total of 750 subjects are required.

Retrospective analyses of clinical study data ([Talbot, et al., 2012](#)) indicate the point estimates for Early Clinical Response at Day 4 range from 72% to 81%. In addition, a recent clinical study of oral solithromycin compared to moxifloxacin found 78% of subjects had an Early Clinical Response of success. Thus, it is reasonable to assume that in a prospective study of subjects with moderate to severe CABP, the rate of Clinical Success at an early time point will be approximately 79%.

For the Early Clinical Response primary efficacy endpoint, with 750 subjects in the ITT population, a response rate of 79% for both treatment groups, NI margin of 10%, a 1-sided alpha level of 0.025, there is a 92% power to show NI. Assuming the microbiological evaluability rate is 27%, a total of 202 subjects are expected to be in the microITT population.

Thus, 750 subjects provide sufficient power for the primary efficacy analyses for both the FDA and EMA regulatory authorities. A summary of the sample size calculations and assumptions is provided in [Table 1](#).

Table 1. Sample Size and Power Calculations

	Primary Outcome (Early Clinical Response)	Secondary Outcome (Early Clinical Response)	Secondary Outcome (Investigator's Assessment of Clinical Response at PTE)	
Population	ITT	microITT	ITT	CE
NI Margin	10%	15%	10%	10%
Evaluability Rate	N/A	27%	N/A	80%
Outcome Rate	79%	80%	79%	85%
PORT Risk Class II	N/A	N/A	15%	15%
N	750	202	638	510
Power	92%	74%	80%	81%

CE = clinically evaluable; ITT = intent-to-treat; microITT = microbiological intent-to-treat; N = number; N/A = not applicable; NI = non-inferiority; PTE = post-therapy evaluation.

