Early Clinical Response and Investigator's Assessment of Clinical Response at PTE will be tested separately and are not co-primary endpoints. The probability for approving an ineffective drug based on PTE efficacy is 1.25%, regardless of the result for the Early Clinical Response endpoint and vice versa. An adjustment would only be required if winning on at least 1 endpoint would result in global approval which is not the case here. In addition, no alpha adjustment is needed for the co-primary efficacy endpoints for the EMA (ITT and CE populations) since NI must be shown in both populations to conclude NI. Hence there will be no adjustment for multiple endpoints.

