For the Early Clinical Response primary efficacy endpoint, with 750 subjects in the ITT population, a response rate of 79% for both treatment groups, NI margin of 10%, a 1-sided alpha level of 0.025, there is a 92% power to show NI. Assuming the microbiological evaluability rate is 27%, a total of 202 subjects are expected to be in the microITT population.

Thus, 750 subjects provides sufficient power for the primary efficacy analyses for both the FDA and EMA regulatory authorities. A summary of the sample size calculations and assumptions is provided in Table 8.

Table 8 Sample Size and Power Calculations

	Primary Outcome (Early Clinical Response)	Secondary Outcome (Early Clinical Response)	Secondary Outcome (Investigator's Assessment of Clinical Response at PTE)	
Population	ITT	microITT	ITT	CE
NI Margin	10%	15%	10%	10%
Evaluability Rate	N/A	27%	N/A	80%
Outcome Rate	79%	80%	79%	85%
PORT Risk Class II	N/A	N/A	15%	15%
N	750	202	638	510
Power	92%	74%	80%	81%

CE = clinically evaluable; ITT = intent-to-treat; microITT = microbiological intent-to-treat; N = number; N/A = not applicable; NI = non-inferiority; PTE = post-therapy evaluation.

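### The EMA claim needs non-inferiority in both ITT and CE, so its power is about 74%, not the 80% and 81% behind the statement that 750 subjects suffice

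*Combined protocol and SAP*

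**What the plan says.** SAP section 5.1.1 treats the EMA objective as a design target: "The study has also been designed to show NI in the co-primary efficacy outcomes for the EMA", namely clinical response at PTE in ITT and in CE-PTE. The ITT calculation is made "assuming an outcome rate of 79% in both treatment groups, NI margin of 10%, 80% power and a 1-sided alpha level of 0.0125", and the result is that "a total of 638 subjects (PORT Risk Class III and IV) are required". For the second population it says: "Assuming an 80% evaluability rate, 510 subjects will be available in the CE population". With 85% success per arm and the same margin and alpha, it then gives 81% power in CE. Dividing by the PORT III/IV share takes 638 to 750 randomised.

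SAP Table 1 and protocol v2.0 Table 8 show 80% and 81% in separate columns. Both documents then state that the size is adequate for both agencies: "Thus, 750 subjects provide sufficient power for the primary efficacy analyses for both the FDA and EMA regulatory authorities" in the SAP, and "Thus, 750 subjects provides sufficient power for the primary efficacy analyses for both the FDA and EMA regulatory authorities" in protocol section 22.13.

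The EMA decision rule is in protocol section 22.4.3. No alpha adjustment is made across the two populations "since NI must be shown in both populations to conclude NI".

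**The concern.** Requiring success on both tests protects the type I error but costs power. The protocol takes the benefit, by making no alpha adjustment, and neither document counts the cost. The 638 was set to reach 80% on the ITT test alone, so nothing is held in reserve for the second test. The power of the both-populations rule cannot exceed the smaller of the two separate powers, and it falls below that unless the two tests almost always agree. The sufficiency statement for the EMA therefore rests on figures that do not describe the EMA decision, and a reader of either table cannot see the actual risk of missing that objective.

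**Working it through.** **Inputs.** From SAP 5.1.1: 79% success per arm in ITT, 85% per arm in CE, margin 10%, one-sided alpha 0.0125, 638 in ITT (319 per arm), 80% evaluable, 510 in CE (255 per arm), Farrington-Manning method. From protocol 22.4.3: the EMA analysis is restricted to PORT III or higher, so 638 and 510 are the relevant numbers, not 750. From protocol 22.1: CE is a subset of ITT.

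**1. Reproduce the plan's figures.** Per-arm size is n = [(z₁₋α·s₀ + z₁₋β·s₁)/Δ]², where s₀ uses the success rates fitted under the null and s₁ the assumed rates.

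- ITT: the restricted rates are 0.7316 and 0.8316, so s₀ = √(0.7316×0.2684 + 0.8316×0.1684) = 0.580. Also s₁ = √(2×0.79×0.21) = 0.576. Then n = [(2.2414×0.580 + 0.8416×0.576)/0.10]² ≈ 318.5, which rounds up to 319 per arm, or 638. Power at 319 per arm is 80.1%.
- CE: the restricted rates are 0.7874 and 0.8874, so s₀ = 0.517, and s₁ = √(2×0.85×0.15) = 0.505. Power at 255 per arm is Φ[(√255×0.10 − 2.2414×0.517)/0.505] = Φ(0.867) = 80.7%.
- 638×0.80 = 510.4, and 638/0.85 = 750.6.

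The plan's separate figures are correct.

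**2. Success rate outside CE.** (0.79 − 0.80×0.85)/0.20 = 0.11/0.20 = 0.55.

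**3. Correlation of the two tests.** With CE nested in ITT, ρ = √[0.80×0.85×0.15/(0.79×0.21)] = √(0.1020/0.1659) = 0.784.

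**4. Joint power, bivariate normal with ρ = 0.784.**

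| Separate powers used | ITT | CE | Both |
|---|---|---|---|
| Farrington-Manning | 80.1% | 80.7% | 73.1% |
| As stated in the plan | 80% | 81% | 73.2% |
| Unpooled variance | 80.5% | 82.1% | 74.2% |

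**5. Simulation check.** 400,000 trials were simulated with 319 per arm, each subject evaluable with probability 0.80, and success 85% if evaluable and 55% otherwise. Both populations were tested with the unstratified Miettinen-Nurminen score statistic. Results: ITT 80.3%, CE 81.2%, both 73.6%, correlation 0.79. With exactly 255 evaluable per arm, joint power is 74.7% and the correlation about 0.82.

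**6. Sensitivity to the correlation** (separate powers 80% and 81%).

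| ρ | 0 | 0.5 | 0.7 | 0.85 | 0.9 | 0.95 | 0.999 |
|---|---|---|---|---|---|---|---|
| Joint power | 64.8% | 69.4% | 71.9% | 74.4% | 75.6% | 77.0% | 79.9% |

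Only near-perfect correlation approaches 80%.

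**7. For scale only.** On the same assumptions, 80% joint power would need about 720 to 730 PORT III/IV subjects, depending on the method. That is 720/0.85 ≈ 847 to 730/0.85 ≈ 859 randomised.

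**The case against.** Every printed number is right. The 80% is tied to ITT and the 81% to CE, no joint power is claimed, and the documents set no joint-power target, so whether the size is sufficient is a matter of judgement. This SAP is the FDA plan: its PTE intervals are descriptive, and the EMA analysis belongs to a separate SAP that is not available here and may state the joint figure. The calculation also ignores the stratification of the EMA interval and assumes the same evaluability and the same non-CE success rate in both arms. Nothing in the analysis would be biased.

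Much of this is fair. The separate powers do stand, the point concerns planning rather than validity, and the modelling assumptions need to be disclosed. But the statement of adequacy for the EMA is printed in both of these documents, next to figures that do not match the rule in protocol 22.4.3, and text in another document would not correct it. If adequacy is a judgement, the reader needs the figure that bears on it. The assumptions may move the result slightly; the objection itself does not contend that they restore 80%.

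**Conclusion.** The concern holds. On the plan's own inputs, the power to meet the EMA objective is about 74% (73.1% to 74.7% across methods). The risk of missing it when the drugs are equal is about 26% (100 − 73.6 = 26.4 in the main simulation), against 20% for the ITT test alone. The result assumes no true difference in either population, equal evaluability and equal non-CE success in the two arms, and unstratified intervals. The decision not to adjust alpha is correct, and the 92% for the FDA endpoint (91.7% when recomputed at 375 per arm) is not affected.

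**What to change.** Add a row or column to SAP Table 1 and protocol Table 8 for the EMA co-primary analysis, ITT and CE jointly, with power of about 74%. Footnote the implied 55% success rate outside CE, the correlation of about 0.78, and the assumptions of equal arms and no stratification. Label it clearly, because the 74% already in both tables is the microITT power and agrees only by coincidence.

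Then amend the sufficiency sentence in both documents so that it either quotes the joint figure for the EMA or is limited to the FDA endpoint. Quoting the figure is preferable, because the 750 was derived from the EMA endpoint and the rationale should keep showing that. If the separate EMA SAP already gives a joint power, use the same number here.

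The cost is one table entry and one sentence per document, and a stated figure that looks somewhat less favourable. Enrolment, margin, alpha and analysis methods stay as they are.

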5.1.2 Randomization and Masking

All eligible subjects will be randomized via an Interactive Response System (IxRS) that assigns them to 1 of the 2 treatment arms omadacycline and moxifloxacin (in a 1:1 ratio). The site delegate will contact the IxRS (via web) after confirming that the subject fulfills all the inclusion criteria and has none of the exclusion criteria. The IxRS will assign a test article to the subject based on a computer-generated randomization schedule. The randomization will be a blocked randomization sequence stratified by PORT Risk Class (II and III/IV), receipt of an allowed antibacterial therapy in the 72 hours prior to study treatment (yes and no), and geographic region (Western Europe/North America, Eastern Europe and Rest of World). Subjects randomized into the study will be assigned the treatment corresponding to the next available number in the respective stratum of the computer-generated randomization schedule. The subject is considered randomized when the IxRS provides the test article assignment (ie, completes a randomization transaction), regardless of whether the subject actually receives any medication. Randomization of subjects with a PORT Risk Class of II will be capped at 15% of the total number of subjects randomized. Randomization of subjects who have received an allowed antibacterial therapy in the 72 hours prior to study treatment will be capped at 25% of the total number of subjects randomized.

5.2 Efficacy Measures

5.2.1 Primary Efficacy Outcome

The primary efficacy outcome is the determination of the response to therapy at the Early Clinical Response assessment (72 to 120 hours after administration of the first dose of test article) and will be determined programmatically using the investigator's assessment of the subject's symptoms associated with CABP entered into the eCRF. The severity of the subject's CABP symptoms of cough, sputum production, pleuritic chest pain, and dyspnea will be evaluated on a 4-point scale (absent, mild, moderate, or severe) based upon the

Community-Acquired Bacterial Pneumonia Subject Symptom Severity Guidance Framework for Investigator Assessment in [Table 2](#).

Table 2. Community-Acquired Bacterial Pneumonia Subject Symptom Severity Guidance Framework for Investigator Assessment

COUGH?	Absent	Mild	Moderate	Severe
	No cough or resolution (to pre-CABP Baseline)	Cough present but it does not interfere with subject's usual daily activities	Cough present, frequent and it does interfere with some of the subject's usual daily activities	Cough is present throughout the day and night; it limits most of the subjects' usual daily activities and sleep patterns
PLEURITIC CHEST PAIN?	Absent	Mild	Moderate	Severe
	No chest pain or resolution of chest pain related to CABP	Chest pain present occasionally with deep breathing but it does not interfere with subject's usual daily activities	Chest pain is present with normal breaths and it does interfere with the subject's usual daily activities	Chest pain is present at rest and/or with shallow breathing; it limits most of the subject's usual daily activities
SHORTNESS OF BREATH?	Absent	Mild	Moderate	Severe
	No shortness of breath or resolution (to pre-CABP Baseline)	Shortness of breath with strenuous activities only but it does not interfere with subject's usual daily activities	Shortness of breath with usual activities and it does interfere with the subject's usual daily activities	Shortness of breath with minimal exertion or at rest; it limits most of the subject's usual daily activities
PHLEGM/ SPUTUM PRODUCTION?	Absent	Mild	Moderate	Severe
	No coughing up of phlegm/sputum or resolution (to pre-CABP Baseline)	Subject coughs up a small amount of phlegm/sputum	Subject coughs up a moderate amount of phlegm/sputum	Subject coughs up a large amount of phlegm/sputum

The categories of Early Clinical Response are defined as follows:

Clinical Success: survival with improvement of at least 1 level (ie, severe to moderate, moderate to mild, mild to absent) compared to baseline (Screening) in at least 2 CABP symptoms (cough, sputum production, pleuritic chest pain, and dyspnea) with no worsening by at least 1 level in the other CABP symptoms. In order for the subject to be considered a Clinical Success, the subject may not meet any criteria for Clinical Failure or Indeterminate Early Clinical Response.

Clinical Failure: meeting any of the following criteria:

- There is no improvement by at least 1 level (ie, severe to moderate, moderate to mild, mild to absent) compared to baseline (Screening) in 2 CABP symptoms.

- Any of the 4 CABP symptoms is worse (by at least 1 level) compared to baseline (Screening).
- The subject requires alternative (rescue) antibacterial treatment for CABP prior to the Early Clinical Response assessment related to either (a) progression or development of new symptoms attributable to CABP or (b) development of infectious complications of CABP (eg, empyema, lung abscess).
- The subject is receiving antibacterial therapy that may be effective for the infection under study for a different infection from the one under study.
- Discontinued study therapy due to an AE prior to the Early Clinical Response assessment.
- Death prior to the Early Clinical Response assessment.

Indeterminate: the clinical response to test article could not be adequately inferred due to:

- Subject was not seen for the evaluation because s/he withdrew consent, were lost to follow-up, other reason (specify).
- Other specified reason.

Subjects with missing data such that an Early Clinical Response cannot be determined will be considered an indeterminate response. Subjects who did not have at least 2 symptoms of CABP at baseline will also be considered an indeterminate response. Since subjects with an indeterminate response are included in the denominator of the calculation of Clinical Success, these subjects are essentially Clinical Failures. For the ITT population, the proportion of ITT subjects with a Clinical Success is defined using the following formula:

$$\frac{\text{Number of subjects with an Early Clinical Success}}{\text{Number of subjects with an Early Clinical Failure} + \text{Number of subjects with a response of Indeterminate} + \text{Number of subjects with an Early Clinical Success}}$$

